	
appropriately. For patients unable to access IV iron therapy, Sponsor will support the iron therapy.
 
During last four weeks of the titration period, the Hb level will be evaluated to meet the inclusion criteria to conduct the randomization similar to observation period. Patients with stable Hb maintained between 10 and 12 g/dl and on stable Eprex[®] dose will proceed to enter the maintenance phase at the end of the titration period. The last four weeks of the titration phase will be considered the baseline period, and Hb levels measured during baseline period will be considered as baseline level.
 
Maintenance Phase
 
The IV dose has to be adjusted individually to maintain hemoglobin between 10 - 12 g/dl. The hemoglobin, hematocrit, and dose will be monitored every two weeks during the maintenance phase. Investigators will decide to change or maintain the dosage of Eprex[®] or PDA10 every four weeks based on Hb level. The dosage will be determined according to the dose adjustment scheme below, and if hemoglobin level is not increased by more than 1 g/dl in any 2-week period or is not approaching 12 g/dl or below 10 g/dl, the dose will be maintained.
 
The maintenance dose should be individualized and the recommended total weekly dose should not exceed 300 IU/kg.
 
Dose adjustment scheme
 
If the hemoglobin increases by more than 1 g/dl in any 2-week period or the hemoglobin is approaching 12 g/dl, the dose should be reduced by approximately 25%. If the hemoglobin continues to increase or exceed 12 g/dl, the treatment should be temporarily withheld until the hemoglobin begins to decrease, at which point therapy should be reinitiated at a dose approximately 25% below the previous dose. If dose reduction is needed, the amount given per dose or the number of weekly injections will be reduced, or both will be reduced.
 
If the hemoglobin is below 10 g/dl, the dose should be increased by approximately 25%.
 
When a change in Eprex[®] or PDA10 dose is indicated, a one-step change (25% of current dosage) is performed according to the stepwise dosing schedule refer to appendix III.
 
The dose adjustment scheme in Open-Label Extension phase is same as maintenance phase, but hemoglobin will be assessed every 4 weeks.

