7.4. RISK AND BENEFITS

The risks of this clinical study are essentially the risk of experiencing an adverse event following administration of PDA10.

The anemia of chronic renal failure can be corrected fully with erythropoietin. In balancing the benefits and the risks, however, the common practice is to aim at partial correction. A linear increase in the hemoglobin concentration or packed cell volume leads to an exponential rise in the viscosity of whole blood (Schaefer RMI et al. 1988, Mayer G et al. 1988, and MacDougall IC et al. 1989), which, in turn, is thought to contribute to many of the adverse events of treatment with erythropoietin such as hypertension, increased peripheral resistance, thrombotic complications, etc. However, this partial correction of the anemia seems to cause near maximal improvement in wellbeing, exercise capacity (Mayer G et al. 1988), and symptoms of anemia. Moreover, the use of erythropoietin has been associated with a reduced need for blood transfusion, reduction in the frequency and severity of anemia-associated morbidity, and improvement in quality of life

The target hemoglobin concentration most commonly used is in the range of 10.0-12.0 g/dl, at which the ratio of risk to benefit seems to be minimized, though some flexibility is necessary in treating individual patients. Because the main aim of treatment with erythropoietin is to reverse the symptoms of anemia, differing thresholds at which this occurs may influence the appropriate final hemoglobin concentration.

With regard to the rate of rise of the hemoglobin response, for most patients an increase of 1 g/dl per month seems sensible. Exceeding this limit may predispose the patients to an increase risk of adverse events, and there is rarely any indication for more rapid correction of anemia.

On the other hand, PDA10 has been never tried in patients with CRF. Therefore, the design of this study excludes the subjects who are considered to have risks based on the current clinical procedures and eliminate the risk of the subjects as much as possible through the strict safety monitoring.

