- If Hb level increase in the past two weeks is < 0.3 g/dL and Hb level is below 10 g/dL, the dose will be increased by 25% of current dosage.
- If Hb increase in the past 2 weeks is ≤ 1.0 g/dL and Hb level is in the target range (10 – 12 g/dL), the dose will be maintained.

When a change in Eprex[®] dose is indicated, a one-step change (25% of current dosage) is performed based on the stepwise dosing schedule refer to appendix III.

* The patients will be treated with iron therapy based on iron level as follows;

- ① Marginal iron store (all patients will have serum ferritin level > 100 to be eligible for entry) -

Eprex[®] dose increasing during the titration phase and IV iron as appropriate. For patients unable to access IV iron therapy, sponsor will support the iron therapy.

- ② Hb is below 10 g/dl and serum ferritin level > 500 - Eprex[®] dose increasing during the titration phase and a close iron monitoring. If serum ferritin is to decline rapidly, giving IV iron should be considered appropriately. For patients unable to access IV iron therapy, sponsor will support the iron therapy.

During last four weeks of the titration period, the Hb level will be evaluated to meet the inclusion criteria to conduct the randomization as same as observation period. Patients with stable Hb maintained between 10 and 12 g/dl and on stable Eprex[®] dose will proceed to enter the maintenance phase at the end of the titration period. The last four weeks of the titration phase will be considered the baseline period, and Hb levels measured during baseline period will be considered as baseline level.

3) Maintenance Phase:

The IV dose has to be adjusted individually to maintain hemoglobin between 10 - 12 g/dl. The hemoglobin, hematocrit, and dose will be monitored every two weeks during the maintenance phase. Investigators will decide to change or maintain the dosage of Eprex[®] or PDA10 every four weeks based on Hb level. The dosage will be determined according to the dose adjustment scheme below, and if hemoglobin level is not increased by more than 1 g/dl in any 2-week period or is not approaching 12 g/dl or below 10 g/dl, the dose will be maintained. The maintenance dose should be individualized, and the recommended total weekly dose should not exceed 300 IU/kg.

Suggested Target Hemoglobin level Range:

10 g/dl to 12 g/dl

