During the study, Hb, Hematocrit and dose of Eprex[®] or PDA10 will be monitored every two weeks. Prior to and during the study, the patient's iron stores, including transferrin saturation (serum iron divided by iron binding capacity) and serum ferritin, will be evaluated.

Dose Adjustment Scheme:

If the hemoglobin increases by more than 1 g/dl in any 2-week period or the hemoglobin is approaching 12 g/dl, the dose should be reduced by approximately 25%. If the hemoglobin continues to increase or exceed 12 g/dl, the dose should be temporarily withheld until the hemoglobin begins to decrease, at which point therapy should be reinitiated at a dose approximately 25% below the previous dose. If dose reduction is needed, either the amount given per dose or the number of weekly injections will be reduced, or both will be reduced.

If the hemoglobin is below 10 g/dl, the dose may be increased by approximately 25% of the previous dose.

When a change in Eprex[®] or PDA10 dose is indicated, a one-step change (25% of current dosage) is performed according to the stepwise dosing schedule refer to appendix III.

The dose adjustment scheme in Open-Label Extension phase is same as maintenance phase, but hemoglobin will be assessed every 4 weeks.

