10.5.3.4. Clinical Laboratory Determinations

Samples for hematology and biochemistry assessments will be collected at every visit and the assessments will be conducted at the central laboratory or local laboratory. At Screening (Visit 1), the Investigator will assess the clinical significance of any values outside the reference ranges provided by the central laboratory; subjects with abnormalities judged to be clinically significant will be excluded from the study.

However, blood test for hemoglobin and hematocrit level can be conducted by the central laboratory. Biweekly basis data for hemoglobin and hematocrit level should be recorded on eCRF until the end of the Maintenance Phase.

HIV test will be conducted at Screening Visit (Visit 1), and CRP, PTH and iron state (Fe, ferritin, transferritin saturation) will be tested at Screening Visit (Visit 1), Baseline Visit (Visit 4), Week 12 (Visit 7), Week 28/Withdrawal (Visit 11), Week 40 (Visit 14) and Week 52/Withdrawal (Visit 17).

Hematology: Hb, Hct, RBC, WBC, Plt, WBC diff count, PT/PTT

Serum biochemistry: Na, K, Cl, total CO₂, Ca, P, ALT/AST, Alkaline phosphatase, Total bilirubin, Glucose, Albumin, Total cholesterol, BUN, Serum creatinine, Uric acid

Iron evaluation: Fe, ferritin, transferritin saturation

* Vitamin B12 and Folate evaluation will be conducted at Screening Visit (Visit 1).

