- Adverse events
- PDA10 or Eprex[®] administration
- Assessment of compliance

Visit 7a (Week 14)

Clinical laboratory test for Hb and Hct will be performed.

Visit 8 (Week 16)

The following procedures will be conducted at this visit:

- Physical examination
- Vital signs (pulse and systolic and diastolic BP)
- Weight
- Blood sample for clinical laboratory values (Hematology/Serum biochemistry)
- Concomitant drugs
- Adverse events
- PDA10 or Eprex[®] administration
- Assessment of compliance

Visit 8a (Week 18)

Clinical laboratory test for Hb and Hct will be performed.

Visit 9 (Week 20)

The following procedures will be conducted at this visit:

- Physical examination
- Vital signs (pulse and systolic and diastolic BP)
- Weight
- Blood sample for clinical laboratory values (Hematology/Serum biochemistry)
- Concomitant drugs
- Adverse events
- PDA10 or Eprex[®] administration
- Assessment of compliance

Visit 9a (Week 22)

Clinical laboratory test for Hb and Hct will be performed.

Visit 10 (Week 24)

The following procedures will be conducted at this visit:

- Physical examination
- Vital signs (pulse and systolic and diastolic BP)
- Weight
- Blood sample for clinical laboratory values (Hematology/Serum biochemistry)
- Concomitant drugs
- Adverse events
- PDA10 or Eprex[®] administration
- Assessment of compliance

Visit 10a (Week 26)

Clinical laboratory test for Hb and Hct will be performed.

Visit 11 (Week 28/Withdrawal)

The following procedures will be conducted at this visit:

- Physical examination
- Vital signs (pulse and systolic and diastolic BP)
- Weight
- Blood sample for clinical laboratory values (Hematology/Serum biochemistry, CRP, PTH, Iron evaluation, Anti-erythropoietin antibody, Serum pregnancy test)
- Chest X-ray
- Concomitant drugs
- Adverse events
- PDA10 administration (subjects who participate in the OLE phase only)
- Assessment of compliance

* Visit 11 at Week 28 will serve as the entry visit for the open label extension phase.

Subjects who signed the ICF will perform the next visit.

Subject who will NOT be participated in the extension phase will be returned to the standard treatment provided at the hospital/clinic respectively.

Visit 12 (Week 32)

The following procedures will be conducted at this visit:

- Physical examination
- Vital signs (pulse and systolic and diastolic BP)
- Weight
- Blood sample for clinical laboratory values (Hematology/Serum biochemistry)
- Concomitant drugs
- Adverse events

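### The open-label extension keeps a 2-week haemoglobin-rise trigger while haemoglobin is measured every 4 weeks, and the synopsis sets no order between the reduce and increase rules

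*Protocol*

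**What the plan says.** **Reduction rule.** The maintenance scheme in Section 10.4.4 reads: "hemoglobin increases by more than 1 g/dl in any 2-week period or the hemoglobin is approaching 12 g/dl, the dose should be reduced". The step is about 25%. The synopsis has the same rule. Above 12 g/dl, treatment is withheld until Hb starts to fall.

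**Extension.** Synopsis and Section 10.4.4 both state: "The dose adjustment scheme in Open-Label Extension phase is same as maintenance phase, but hemoglobin will be assessed every 4 weeks". Section 10.5.3.4 confirms that the 2-weekly series stops: "Biweekly basis data for hemoglobin and hematocrit level should be recorded on eCRF until the end of the Maintenance Phase". The schedule in Section 10.5.5.1 lists extension visits at Weeks 32, 36, 40, 44, 48 and 52 only.

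**Increase rule.** The synopsis says: "If the hemoglobin is below 10 g/dl, the dose should be increased by approximately 25" per cent. Section 10.4.4 says: "If the hemoglobin is below 10 g/dl, the dose may be increased by approximately 25% of the previous dose". Neither states which rule prevails when both are met. The titration rule in Section 10.4.4 is different. It allows an increase only under a joint condition: "If Hb level increase in the past two weeks is < 0.3 g/dL and Hb level is below 10 g/dL".

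**Rationale.** Section 7.4 says of the rate of rise that "for most patients an increase of 1 g/dl per month seems sensible", and that going faster may raise the risk of adverse events.

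**The concern.** A rate-of-rise rule needs two readings at the interval it names. The extension sentence changes the measuring interval and leaves the trigger as it was, so at most extension visits a site cannot tell whether the rule applies. The patient most exposed is one whose Hb is rising quickly but is still below 10 g/dl. The reduction cannot be demonstrated, the 12 g/dl rules are not reached, and the remaining instruction is to raise the dose. That runs against the purpose of the rule, in a phase that exists to assess long-term safety and in which every patient receives PDA10.

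In maintenance the readings are available, but the synopsis gives a patient who meets both conditions two opposite instructions of equal force.

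**Working it through.** **1. Which readings exist.** In maintenance, Hb is taken every 2 weeks through Weeks 24, 26 and 28, so a 2-week change is available at each dose decision, including Week 28. In the extension the preceding reading is always 4 weeks old. Week 32 is the first visit affected. Week 52 lists no dosing, so five dosing visits are concerned (Weeks 32 to 48).

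**2. What a 4-week change proves.** Let d1 and d2 be the two 2-week changes and D = d1 + d2.
- If D > 2, the larger of d1 and d2 is at least D/2 > 1, so the trigger is proven.
- If D ≤ 2, it is undetermined. D = 1.5 may be 0.75 + 0.75 (not met) or 0.2 + 1.3 (met).

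Example: Hb is 8.5 at Week 32, 8.6 at Week 34 (not measured) and 9.8 at Week 36. The last 2-week rise is 1.2, so the trigger is met, but the site sees a 4-week rise of 1.3 and a value below 10. Only the increase rule is left.

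**3. The two synopsis rules together.** A change from 8.6 to 9.8 g/dl in 2 weeks is a rise of 1.2 > 1 (reduce) that ends at 9.8 < 10 (increase). On a grid of previous and current Hb from 7.0 to 13.0 in steps of 0.1, 190 pairs meet both rules. Under the titration rules none do. In Section 10.4.4 the pair is *should* reduce against *may* increase, which largely lets the reduction win, though no order is written.

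**4. How many patients.** The protocol gives no visit-level Hb variability. Section 10.6.7.2 assumes SD 1.1 g/dl for the change between the baseline and evaluation means, each based on three readings (Weeks -4, -2, 0 and 24, 26, 28). Assume a first-order autoregressive series with visit SD σ and 2-week correlation ρ. Then

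Var(change) = 2σ²(v − c), with v = (3 + 4ρ + 2ρ²)/9 and c = (ρ¹² + 2ρ¹³ + 3ρ¹⁴ + 2ρ¹⁵ + ρ¹⁶)/9,

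so σ = 1.1 / √(2(v − c)).

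The counts below come from 600,000 simulated patients per row, with mean Hb 11 g/dl and no dose feedback. *Maintenance* means both rules met at least once over six decisions (Weeks 4 to 24). *Extension* means, at least once over five dosing visits, Hb < 10, last 2-week rise > 1 and 4-week rise ≤ 2. The extension size of 252 = 2 × 126 is assumed.

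| ρ | v | c | σ | Maintenance, of 316 | Extension, of 252 |
|---|---|---|---|---|---|
| 0.60 | 0.680 | 0.001 | 0.94 | 5.2 | 3.4 |
| 0.75 | 0.792 | 0.019 | 0.88 | 2.6 | 1.7 |
| 0.90 | 0.913 | 0.231 | 0.94 | 0.7 | 0.5 |

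If σ is instead taken freely from 0.8 to 1.2, the counts run from 0.1 to 16.5 of 316 (5.8 at σ = 1.0, ρ = 0.75) and from 0.1 to 10.7 of 252 (3.8).

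**5. How often the extension trigger is provable.** Of rises above 1 g/dl in the last 2 weeks, the 4-week rise exceeds 2 g/dl in 2% to 16% at the implied σ (9% at ρ = 0.75), and in 0.6% to 25% over the wider range.

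**6. A 4-week trigger of more than 1 g/dl.** It finds 56% to 57% of those rises at the implied σ (53% to 60% over the wider range). Of its flags, 29% to 76% contain no 2-week rise above 1 g/dl (18% to 86% over the wider range).

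**The case against.** The case for leaving the text alone has substance. Investigators decide individual doses, changes are one step, and increases come at most once in 4 weeks. The approaching-12 and above-12 rules work at every extension visit, blood pressure is checked there, and unscheduled visits are allowed. The Section 7.4 remark concerns the correction of anaemia and is not a formal limit for stabilised patients. All this stands and keeps the point minor. It does not make the trigger measurable: unscheduled visits respond to events and do not supply the missing mid-interval reading.

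The objection also succeeds against a wider remedy. Copying the titration guard into maintenance, so that the dose is held when Hb is below 10 g/dl and rising by 0.3 to 1.0 g/dl, would alter blinded dosing for about 35 of 316 patients at σ = 1.0, ρ = 0.75, against about 6 with the clash. Titration and maintenance treat different patients, so different rules by phase are a legitimate choice. A reader might infer that the guard was left out by mistake; the documents do not show that.

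Two other stronger readings are tempting:
- **Bias in the co-primary weekly dose.** Nothing supports this. The maintenance scheme is the same in both blinded arms, the overlap is rare, and Section 10.6.4.1 makes the extension analysis descriptive only.
- **An extension without upper protection.** This is not so, because the 12 g/dl rules remain usable.

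**Conclusion.** The point holds as a minor safety and wording defect. The extension rule cannot be evaluated as written on scheduled Hb unless the 4-week rise exceeds 2 g/dl, and synopsis and body differ on the force of the increase rule. These two statements follow from the text and need no assumption.

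The size does rest on assumptions: the autoregressive form, mean 11 g/dl, no dose feedback, 252 patients entering the extension, and a visit SD back-calculated from the planning SD of 1.1. On that footing roughly 1 to 5 of 316 patients are affected in maintenance and roughly 1 to 3 of 252 in the extension. These are orders of magnitude only. The maintenance half is the weaker one, because the wording of Section 10.4.4 already points to the reduction.

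**What to change.** **Synopsis and Section 10.4.4, maintenance.** Use *may be increased* in both texts and add: *If Hb has risen by more than 1 g/dl in 2 weeks, the reduction prevails and the dose is not increased, whatever the Hb level.* Do not add a hold rule for rises of 0.3 to 1.0 g/dl to the blinded phase.

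**Extension.** Restate the trigger on the interval actually measured, for example: *If Hb has risen by more than 1 g/dl since the previous 4-weekly visit, do not increase the dose; reduce it by one step.* This agrees with the monthly rate in Section 7.4. A threshold of 2 g/dl in 4 weeks would find nothing that the present rule does not already prove. The sponsor's clinicians should confirm the threshold.

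**Cost.** A few sentences in a protocol amendment, with IRB/IEC approval before use (Section 10.7.1). No new visit, sample or patient is needed. The 1 g/dl threshold still misses some fast 2-week rises, and it will reduce the dose of some patients who had none, but each of those patients has risen by more than 1 g/dl over the 4 weeks.

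### The open-label extension keeps a dose-reduction condition based on a 2-week hemoglobin rise but schedules hemoglobin only every 4 weeks, so that condition cannot be evaluated there

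*Protocol*

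**What the plan says.** **Reduction and withholding.** The dose adjustment scheme in Section 10.4.4 calls for a reduction on either of two conditions: "If the hemoglobin increases by more than 1 g/dl in any 2-week period or the hemoglobin is approaching 12 g/dl". Withholding is worded separately: "If the hemoglobin continues to increase or exceed 12 g/dl, the dose should be temporarily withheld until the hemoglobin begins to decrease". A value below 10 g/dl leads to an increase. The maintenance paragraph of the same section keeps the dose unchanged by reference to the same conditions, including the absence of a rise above 1 g/dl over 2 weeks.

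**Extension.** Section 10.4.4 carries the scheme over: "The dose adjustment scheme in Open-Label Extension phase is same as maintenance phase, but hemoglobin will be assessed every 4 weeks". The synopsis (Dosage) says the same. The schedule in Section 10.5.5.1 and the visit descriptions in 10.5.5.2 place extension visits at Weeks 32, 36, 40, 44, 48 and 52, with no intermediate Hb visits. Footnote 8 of the schedule gives a visit window of plus or minus 5 days.

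**Maintenance.** Measurement is 2-weekly: "The hemoglobin, hematocrit, and dose will be monitored every two weeks during the maintenance phase". Dose decisions are made "every four weeks based on Hb level".

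**Other statements on timing.**
- Section 10.4.4, just before the dose adjustment scheme, says in general terms that Hb is monitored every two weeks during the study.
- Section 10.5.3.4 ends the 2-weekly recording of Hb with the maintenance phase.
- The titration text in Section 10.4.4 allows dose changes sooner than 4 weeks when Hb or its rate of change is outside the safety limits.
- Footnote 2 of the schedule restricts only dose increases to once per 4 weeks.

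**The concern.** A rule that depends on a 2-week change needs values 2 weeks apart. The extension takes over the rule and halves the measurement frequency in the same sentence. A site following the text cannot establish whether the rate condition has been met, nor whether the matching condition for leaving the dose alone has been met.

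The protocol itself treats rate of rise as a safety matter. Section 7.4 says that a rise faster than about 1 g/dl per month may increase the risk of adverse events, and that PDA10 has not previously been given to patients with chronic renal failure. Under Section 10.2 everyone in the extension receives PDA10, so patients coming from the Eprex arm have their first exposure under the sparser schedule. The extension's stated aim is long-term safety and tolerability (Section 8). If sites resolve the gap in different ways, part of the dosing behind those safety data follows no common rule.

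**Working it through.** The protocol gives no figure to reproduce. The check sets the conditions against the visit schedule.

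**Step 1. Spacing of Hb values in the extension.** From the entry visit at Week 28, values fall at Weeks 32, 36, 40, 44, 48 and 52: 6 values and 6 gaps of 4 weeks. Scheduled pairs 2 weeks apart: 0. With both visits at the limits of the window, a gap runs from 28 − 5 − 5 = 18 days to 28 + 5 + 5 = 38 days. Even the shortest gap exceeds 14 days.

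**Step 2. What a 4-week change reveals.** Write the change over exactly 28 days as D = x1 + x2, the two successive 2-week changes. The condition is met if x1 > 1 or x2 > 1.
- If D > 2 g/dl, at least one half must exceed 1.
- If D ≤ 2 g/dl, the answer is undetermined. For D = 1.5, the split 0.75 + 0.75 does not meet the condition over the two halves, while 1.2 + 0.3 does.
- The 2 g/dl figure holds only for a gap of exactly 28 days. Over 38 days, a steady rise of exactly 1.0 g/dl per 14 days gives 38/14 × 1.0 = 2.71 g/dl without meeting the condition.

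So no fixed cut-off on the 4-weekly change stands in for the written condition.

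**Step 3. Each condition against the extension schedule.**

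| Condition | Depends on | Checkable at 4-weekly values? |
|---|---|---|
| Reduce: rise > 1 g/dl in 2 weeks | 2-week change | No |
| Reduce: approaching 12 g/dl | Level | Yes, though the protocol gives no number for approaching |
| Withhold: above 12 g/dl | Level | Yes |
| Withhold: continued rise | Direction, no interval named | Yes, between scheduled values |
| Restart: Hb begins to fall | Direction, no interval named | Only at the next scheduled value |
| Increase: below 10 g/dl | Level | Yes |
| Keep dose: no rise > 1 g/dl in 2 weeks | 2-week change | No, for this part |

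**Step 4. The same test in maintenance.** Values at Weeks 2 to 28 in steps of 2 give 14 post-baseline values and, counting from Week 0, 14 two-week changes. If the 4-weekly decisions fall at Weeks 4, 8, …, 28, there are 7 of them, and each can look back on 14/7 = 2 two-week changes. The rate condition can be evaluated. The other 14 − 7 = 7 values (Weeks 2, 6, 10, 14, 18, 22, 26) fall between decisions. Action on a crossing there would wait about 2 weeks if the 4-weekly wording is read strictly.

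**Step 5. Is the strict reading required?** The maintenance text lacks the early-change clause found in the titration text, which favours it. Footnote 2 limits only increases, which suggests that an earlier reduction is open. The document does not settle the matter.

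**Step 6. Monitoring interval.** The general 2-weekly statement in Section 10.4.4, read literally, covers the extension. The extension sentence in the same section, the schedule, and the end of 2-weekly recording in Section 10.5.3.4 all say otherwise.

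**The case against.** The strongest reply is that only one limb of a multi-limb rule fails. The level conditions work at 4-weekly visits, and a patient rising quickly will often soon be near 12 g/dl, where the level condition leads to the same reduction. This stands, and it narrows the group affected to patients whose Hb is rising fast but is not yet near 12 g/dl. It does not make the rate condition assessable.

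It can also be said that the 4-weekly interval is deliberate, since the extension sentence was added by amendment (Section 20), and that Section 10.3.3 allows temporary discontinuation and Section 10.5.5.2 provides for unscheduled visits. These give an investigator room to act. None of them requires an Hb value 2 weeks after the last one, and a deliberate interval still has to match the rule applied to it. The general 2-weekly statement sits under the maintenance heading and may have been meant for that phase only, but its wording does not say so.

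Three stronger readings are tempting, and the document does not support them:
- **That withholding also rests on a 2-week change.** It rests on a continued rise or a level above 12 g/dl.
- **That the rate condition fails in maintenance too.** Hb is measured 2-weekly there. What is open is the timing of action, and footnote 2 counts against a bar on earlier reductions.
- **That a 4-week rise above 2 g/dl settles the question.** The visit window defeats that, as shown above.

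**Conclusion.** The point holds for the extension. The 2-week rate condition for reduction, and its counterpart for leaving the dose unchanged, cannot be evaluated from any of the six scheduled extension values, whether visits are on time or anywhere within the window. The remaining conditions can be checked every 4 weeks, with the start of a fall after withholding visible only at the next scheduled value. It would go too far to conclude that the safety rules as a whole cannot work.

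Two inconsistencies accompany it: the general 2-weekly monitoring statement against the 4-weekly extension interval, and the unstated position on maintenance dose changes between 4-weekly decisions. The second is an ambiguity with a possible delay of about 2 weeks under the strict reading, not a rule that fails.

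This should be corrected because it concerns a safety-related dosing rule. It is not a threat to the trial's main conclusion: Section 10.6.4.1 makes the extension analysis descriptive only, so the extension problem leaves the equivalence analysis and the sample size as they are. The conclusion assumes that Hb is obtained at scheduled visits. How many patients would be affected cannot be derived from the protocol.

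**What to change.** Reconcile the synopsis (Dosage), Section 10.4.4 (titration, maintenance and dose adjustment scheme), Section 10.5.3.4, and the schedule with its footnotes 2 and 8 in Section 10.5.5.1, so that:

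1. the dose-adjustment conditions in the extension, including those for leaving the dose unchanged and for restarting, can be evaluated on the Hb interval scheduled there;
2. the general monitoring statement names the phase to which it applies;
3. the text states consistently when maintenance dose decisions may be made, including what follows from a value obtained between two 4-weekly decisions.

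Which rule and which interval apply is for the sponsor's clinicians to decide. The cost is a wording amendment. If the reconciliation changed the visit schedule, further sampling would follow from that choice.
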